6.6.2 Toxicity Management and Dose Modification Recommendations for Nivolumab

AEs (both non-serious and serious) associated with nivolumab exposure may represent an immunologic etiology. These AEs may occur shortly after the first dose or several months after the last dose of treatment. Therefore, early recognition and initiation of treatment is critical to reduce complications.

There will be no dose reductions for nivolumab. Treatment can be delayed for nivolumab related AEs. If the criteria to resume treatment are met, the subject should restart treatment at the next scheduled time point per protocol.

Nivolumab administration should be delayed for the following:

- Grade 2 non-skin, drug-related AE, with the exception of fatigue
- Grade 2 drug-related creatinine, AST, ALT and/or Total Bilirubin abnormalities
- Grade 3 skin, drug-related AE
- Grade 3 drug-related laboratory abnormality, with the following exceptions:
 - Grade 3 lymphopenia or asymptomatic amylase or lipase does not require dose delay
 - Grade ≥ 3 AST, ALT, Total Bilirubin will require dose discontinuation (see Section 6.6.2.1)
- Any adverse event, laboratory abnormality, or intercurrent illness which, in the judgment of the investigator, warrants delaying the dose of study medication.

There are no recommended dose modifications for hypothyroidism or hyperthyroidism. Interrupt or slow the rate of infusion in participants with mild or moderate (Grade 1-2)

infusion reactions. Discontinue nivolumab in participants with severe or life-threatening infusion reactions (Grade 3-4) (see Section 6.6.2.4).

Participants who require delay of nivolumab should be re-evaluated weekly or more frequently if clinically indicated and resume nivolumab dosing when re-treatment criteria are met (see Section 6.6.2.2). The dose modification can occur independently for the 2 drugs used if toxicity can be clearly attributed to one of the drugs. Resumption of regorafenib dosing is not required to receive further nivolumab dosing and vice versa. Treatment with individual drugs (regorafenib or nivolumab) may continue on schedule even if other drug is interrupted or permanently discontinued due to toxicity.

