8.3 Adverse Events and Serious Adverse Events

Progression per se should not be regarded as AE. Instead, the associated signs and symptoms should be recorded as AEs.

The intensity of AEs should be documented using the NCI-CTCAE, v5.0.

The study treatment action should be recorded separately for each study treatment as detailed in the eCRF.

- Drug withdrawn
- Drug interrupted
- Drug delayed
- Dose reduced
- Dose not changed
- Dose increased
- Not applicable
- Unknown

The definitions of an AE or SAE can be found in Section [10.3](#).

AEs will be reported by the participant (or, when appropriate, by a caregiver, surrogate, or the participant's legally authorized representative or health care professional not involved in the study).

The Investigator and any qualified designees are responsible for detecting, documenting, and recording events that meet the definition of an AE or SAE. They remain responsible for following up SAEs, or AEs, considered related to the study intervention or study procedures, or those that caused the participant to discontinue the study (see Section [7](#)).

Investigators should refer to the Safety Information section of the current IB of regorafenib and the current IB of nivolumab for the expected side effects. As with any agent, there is always the potential for unexpected AEs, including hypersensitivity reactions. The IB will be updated if any new relevant safety data are obtained.

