9.4.5 Other Safety Analyse(s)

For all safety analyses, the FAS will be used as the FAS definition matches the one of the safety set. The incidence of TEAE (new or worsening from baseline) will be summarized by system organ class and preferred term, severity (based on CTCAE grades), type of AE and relation to study treatment. Deaths reportable as SAEs and non-fatal serious AEs will be listed by participant and tabulated by type of AE. AEs leading to study treatment discontinuation and/or modifications will be summarized. Laboratory abnormalities will be summarized by severity. Frequency and incidence rates will be provided. Frequency tables will also be provided for changes in severity from baseline to worst value post-baseline. Laboratory data considered as AE will be graded according to CTCAE v. 5.0, if applicable. The following summaries will be generated separately for hematology and biochemistry, overall and by cohort with the same dose:

- Frequency table for newly occurring on-treatment all CTCAE grades and CTCAE Grades 3 or 4
- Shift tables using CTCAE grades to compare baseline to the worst on-treatment value

CCI

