6.5.2 Adverse events

All adverse events (AE) whether considered drug-related or not, will be reported on the CRF with diagnosis, start/stop dates, dates of any grade change, action taken, whether treatment was discontinued, any corrective measures taken, and outcome. For all events, the relationship to treatment and the severity of the event will be determined by the Investigator. AEs will be classified and coded using the National Cancer Institute (NCI) Common Terminology Criteria Adverse Event (CTCAE), version 5.0 .

According to the protocol (See section 8.3.1 of the final study protocol) AE will be collected from the signing of the informed consent form (ICF) until the end of active FU visit, which should be 30 days after last dose of regorafenib and 100 days after last dose of nivolumab. An AE is considered as treatment-emergent (TEAE) if it starts during treatment or within the post-treatment time window.

For further definitions of the terms AE, SAE, seriousness, intensity, causal relationship with treatment, causal relationship to protocol-required procedures, action taken, and outcome please refer to the respective section of the protocol.

In the CRF only the worst action taken with regard to the study medication was captured, if nothing else changed while the AE was ongoing. Therefore all tables using this field, will have a footnote, mentioning this fact.

In addition to standard medDRA grouping, treatment-emergent AE of importance will be defined as follows:

- Rash grade 3 or higher. Rash consists of the following MedDRA LLT*:

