- Overview over treatment-emergent AEs leading to study drug withdrawal
- Treatment-emergent AEs leading to study drug withdrawal by worst CTCAE grade
- Treatment-emergent AEs leading to regorafenib dose reduction
- Treatment-emergent AEs leading to drug interruption
- Treatment-emergent AEs leading to dose reduction and/or drug interruption
- Treatment-emergent AEs of importance
- Overview over treatment-emergent drug-related AEs
- Treatment-emergent drug-related AEs with grades 3, 4, or 5
- Treatment-emergent drug-related AEs by worst CTCAE grade
- Treatment-emergent drug-related AEs occurring in at least 5% of patients
- Overview over treatment-emergent drug-related AEs leading to study drug withdrawal

- Treatment-emergent drug-related AEs leading to study drug withdrawal by worst CTCAE grade
- Treatment-emergent drug-related AEs leading to regorafenib dose reduction
- Treatment-emergent drug-related AEs leading to drug interruption
- Treatment-emergent drug-related AEs leading to dose reduction and/or drug interruption

The incidence of pre-treatment AE and non-treatment-emergent AEs during long-term follow-up will be tabulated. Other non-treatment-emergent AE will be presented by means of a subject data listing only.

Overview tables of adverse events will be presented in addition to the frequency tables.

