6.5.3 Deaths and Serious Adverse events

Serious adverse events (SAE) will be classified using Version 5 of the National Cancer Institute (NCI) Common Terminology Criteria Adverse Event (CTCAE) grading system, and MedDRA terminology.

- Overview over treatment-emergent SAEs
- Treatment-emergent SAEs by worst CTCAE grade
- Treatment-emergent SAEs leading to study drug withdrawal
- Treatment-emergent SAEs leading to study termination
- Treatment-emergent SAEs leading to regorafenib dose reduction
- Treatment-emergent SAEs leading to drug interruption
- Treatment-emergent SAEs leading to dose reduction and/or drug interruption
- Overview over treatment-emergent drug-related SAEs
- Treatment-emergent drug-related SAEs by worst CTCAE grade
- Listing of treatment-emergent SAEs
- Listing of non-treatment-emergent SAEs

The incidence of deaths in the study and especially deaths up to within 30 and 100 days of last dose of Regorafenib and Nivolumab respectively will be summarized by cause of death. All deaths up to within 30 (100) days of last dose of study drug will be listed by patient with start and stop date of study medication, date of death, and cause of death. All deaths beyond 30 (100) days after last dose of study drug will be displayed in a separate listing.

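### The SAP's dose-action tables for AEs and SAEs neither name nor assign actions recorded as 'Drug delayed', the main non-permanent nivolumab modification

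*SAP*

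**What the plan says.** **How the action is recorded.** Protocol 8.3 instructs: "The study treatment action should be recorded separately for each study treatment as detailed in the eCRF". Its list of possible actions has "Drug interrupted" and, as a separate entry, a delayed drug. It also lists withdrawal, reduction, increase and no change. Protocol 6.4 likewise keeps a delayed nivolumab dose apart from an interrupted infusion when reasons are entered in the eCRF.

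**What can happen to nivolumab.** Protocol 6.6.2: "There will be no dose reductions for nivolumab. Treatment can be delayed for nivolumab related AEs". A list of toxicity triggers follows under "Nivolumab administration should be delayed for the following".

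**What the protocol promises to report.** Protocol 9.4.5: "AEs leading to study treatment discontinuation and/or modifications will be summarized". Delays are not excepted.

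**What the SAP tabulates.** SAP 6.5.2 lists, for TEAEs and again for drug-related TEAEs, tables for withdrawal, regorafenib dose reduction, drug interruption, and the composite "Treatment-emergent AEs leading to dose reduction and/or drug interruption". SAP 6.5.3 repeats the pattern for SAEs, ending in "Treatment-emergent SAEs leading to dose reduction and/or drug interruption". The word delay does not appear in the SAP text provided.

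**The concern.** Nivolumab cannot be reduced under this protocol. Short of permanent discontinuation, toxicity mainly shows up as a postponed infusion. If postponed infusions carry their own code and no table reads that code, the action tables miss the commonest route by which the protocol lets an AE change nivolumab treatment.

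The composite is the table most readers would take as the toxicity-driven modification rate for the combination, because its title names neither drug. Safety of the combination is a stated secondary objective, and Protocol 9.5 says a Phase III study is intended, so an understated rate could be carried forward. Regorafenib is touched too: Protocol Table 6-6 describes holding the drug for liver abnormalities as delaying dosing, and SAP 6.5.2 names raised liver enzymes and bilirubin as events of importance.

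**Working it through.** The plan states no figure on this point, so the check is a mapping of recorded actions to tables.

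**Step 1. Protocol 8.3 actions against the SAP 6.5.2 and 6.5.3 tables.**

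| Action recorded | TEAE and drug-related TEAE tables | SAE tables |
|---|---|---|
| Withdrawn | yes | yes |
| Reduced | yes, regorafenib named | yes, regorafenib named |
| Interrupted | yes, drug not specified | yes, drug not specified |
| Delayed | none named | none named |
| Composite | reduction, interruption | reduction, interruption |

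**Step 2. Is there a rule that assigns delays to another row?** SAP 6.5.2 refers to the protocol for the meaning of action taken. The protocol lists the categories but does not define the difference between interrupted and delayed. The SAP has no pooling rule.

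**Step 3. Can the protocol's own rules produce a delay-only AE?** Take a Grade 2 non-skin drug-related AE, other than fatigue, attributed to nivolumab, and outside the toxicities with their own guidance. Protocol 6.6.2 puts it on the nivolumab delay list. Protocol Table 6-3 shows no change to regorafenib at Grade 0-2. The two action fields would read delayed for nivolumab and unchanged for regorafenib. Read by code, that AE is in no action table.

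**Step 4. Does another output supply the missing incidence?**
- SAP 6.5.1 summarises dose modification for each drug but does not tie it to AEs.
- The subject listings of SAP 4.1 show the records but give no incidence.
- The regorafenib/nivolumab/both breakdown in SAP 6.5.2 concerns causality, not which drug was acted on.
- The footnote required in SAP 6.5.2 discloses something else: "In the CRF only the worst action taken with regard to the study medication was captured". How delay ranks among the actions is not given.

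**Step 5. What one participant is worth.** Let d be the number of participants with at least one AE recorded as a delay and no AE recorded as reduction or interruption of either drug. With 70 treated participants, the composite is short by d/70. For d = 1 this is 1/70 = 1.4 percentage points; for d = 3 it is 3/70 = 4.3. If delays are pooled into interruption, the shortfall is 0. The documents give no means of estimating d.

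**The case against.** The strongest reply is that interruption in this protocol is wider than one eCRF code. Sections 4.1.2, 6, 6.6.1 and 6.6.2 all speak of either drug being interrupted because of toxicity. Section 10.6 joins interruption and delay in a single phrase for both drugs, and Table 6-6 places its instruction to delay dosing under a column headed dose interruption. The SAP wording fits this: reduction is confined by name to regorafenib, while interruption is left open to both drugs. A programmer could reasonably count a postponed infusion as an interruption.

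This stands as far as it goes. It means a reader should not infer that interruption applies only to an infusion under way, or that the composite is close to a regorafenib-only result. Neither is established, because both depend on a strict code mapping that the SAP does not state. It does not remove the gap: with two separate codes and no rule, two programmers could produce different counts from the same data.

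Other replies also hold in part. AE-related nivolumab withdrawals and infusion interruptions are tabulated. Protocol 6.6 calls for the more conservative approach to both drugs when attribution is unclear, so some AEs that delay nivolumab will also carry a regorafenib action and be counted. The protocol's safety endpoint is AE incidence and severity, which these tables do not alter. Protocol 9.4.5 asks for a summary of AEs leading to modifications, not a table for each action or each drug.

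**Conclusion.** The point holds as an unassigned category in the safety tables. Delay is recorded as its own action and is the main non-permanent change open to nivolumab, yet no TEAE, drug-related TEAE or SAE action table names it and no rule places it. Under a strict reading of the codes, delay-only AEs fall out of every action table and the composite understates what Protocol 9.4.5 promises. Under a pooled reading nothing is lost. The SAP does not choose between them.

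The size cannot be given. A reader might assume that 15-40% of participants have an AE-related nivolumab delay and that a third to a half of those have no other counted action. That yields 70 x 0.15 / 3 = 3.5 to 70 x 0.40 / 2 = 14 participants, or 5% to 20%. Neither rate is in the documents, so this range should not be used to judge importance. AE incidence and grade, and the ORR test, are untouched. It is a cheap improvement worth making before the tables are programmed.

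**What to change.** In SAP 6.5.2 and 6.5.3:

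1. Reword the composite to cover dose reduction, drug interruption and/or drug delay, for TEAEs, drug-related TEAEs and SAEs.
2. Then do one of two things: add a table of events leading to drug delay for each of those three groups, or state that the interruption tables include actions recorded as delayed for either drug.

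The action is already recorded for each drug under Protocol 8.3, so no new data collection and no change to any dosing rule is needed. The cost is a few tables, or one sentence, and a reported modification rate that may be higher. Separate action tables for regorafenib and nivolumab would be informative but are a matter of presentation and optional.

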4.1.4 Long-Term Follow-Up

[figure not shown]
All surviving participants will enter the long-term FU period after discontinuing from the active FU period except for participants who explicitly withdraw consent or are lost to FU. Participants will be followed for overall survival and subsequent anti-cancer therapy at 3-month intervals (\pm 14 d) until end of study, 2 years after the last participant started study intervention (telephone contact is sufficient) or consent withdrawal or death or lost to FU. Participants may be contacted at additional times throughout the course of the study in order to collect survival data to ensure that long-term FU data is current.

CCI

CCI

patients with mCRC. Primary endpoint for the study is ORR by RECIST, which is an

CCI

CCI

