8.3.1 Time Period and Frequency for Collecting AE and SAE Information

All AEs and SAEs will be collected from the signing of the ICF until the end of active FU visit (30 d after last dose of regorafenib and 100 d after last dose of nivolumab at the time points specified in the SoA (Section [1.3](#))).

Medical occurrences that begin before obtaining informed consent will be recorded on the medical history section of the eCRF. Medical occurrences that begin before the start of study intervention but after obtaining informed consent will be recorded on the AE section of the eCRF. Medical occurrences that started before but deteriorated after obtaining informed consent will be recorded as AEs.

All SAEs will be recorded and reported to the Sponsor or designee immediately and under no circumstance should this exceed 24 hr, as indicated in Section 10.3. The Investigator will submit any updated SAE data to the Sponsor within 24 hr of it being available.

Investigators are not obligated to actively seek AE or SAE after conclusion of the study participation. However, if the Investigator learns of any SAE, including a death, at any time after a participant has been discharged from the study, and he/she considers the event to be reasonably related to the study intervention or study participation, the Investigator must promptly notify the Sponsor.

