10.6 Appendix 6: FU Assessments

Active FU visits

All participants who withdraw from study treatment period for any reason (except death or lost to FU) will be followed for safety at mandatory active FU visits, which will be performed 30 d (+7 d) after the last administration of study treatment regorafenib/nivolumab and 100 d (+7 d) after the last dose of nivolumab.

If the treatment was permanently discontinued after the maximal allowed dose interruption/delay period, 28 d for regorafenib and 6 weeks for nivolumab, the 1st active FU visit should occur within 14 d of the permanent discontinuation. AE assessment and concomitant medication review must be updated at these active follow-up visits and all AEs starting within 30 d after the last dose of study treatment regorafenib (100 d after the last dose nivolumab) should be collected and recorded in the eCRF.

Additionally, for participants who discontinue study treatment without radiological disease progression, drug-related AEs will continue to be collected FU tumor evaluations (by CT or MRI with contrast unless contraindicated) will be performed until radiological progression, occurrence of secondary malignancy and/or start of first subsequent systemic anticancer treatment, whichever comes first, or any other criterion for withdrawal is met.

During the efficacy FU visits, CT/MRI evaluations will be performed at the same intervals as during study treatment (see [Table 1–2](#)). Note: all images still need to be prospectively collected and submitted in DICOM format in case independent central review is needed.

Long-term FU

All participants who withdraw from study treatment period with radiological PD, or from active FU for any reason will be followed for survival and first subsequent anti-cancer treatment, every 3 months (± 14 d) during the long-term FU period, until either data

maturation for the final analysis is reached, or death of the patient, or any other criterion for withdrawal from long-term FU is met. The long-term FU contacts may occur at more frequent intervals at the discretion of the Sponsor. If a patient is lost to FU, the site will try to contact the patient, the patient's relatives, or another doctor treating the patient, unless prohibited by local requirements.

All participants in the long-term FU period will be contacted (telephone contact is sufficient) every month (± 7 d) to determine survival status and obtain information on subsequent systemic anti-cancer treatment.

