4.5 Analysis of long-term follow-up

During the long term follow-up data on survival and subsequent anti-cancer therapies are collected by either telephone contact or onsite visit. After the last patient finished the long-term follow-up, a final analysis of the long-term follow-up will be conducted. This will be conducted on the follow-up set of patients and will include population characteristics, overall survival analysis and anti-cancer medication. Details of the FU analysis will be specified in a separate document, either as addendum to this SAP or in a separate SAP.

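### SAP 6.5.2 plans an AE incidence table for long-term follow-up, where AEs are not sought, and leaves late drug-related AEs in active follow-up to a listing

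*SAP*

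**What the plan says.** **Reporting.** SAP 6.5.2 defines a treatment-emergent event as follows: "An AE is considered as treatment-emergent (TEAE) if it starts during treatment or within the post-treatment time window". The sentence before it gives 30 days after regorafenib and 100 days after nivolumab as the end of AE collection. For events that are not treatment-emergent, the section has two rules. First: "The incidence of pre-treatment AE and non-treatment-emergent AEs during long-term follow-up will be tabulated". Second: "Other non-treatment-emergent AE will be presented by means of a subject data listing only". SAP 6.5.3 adds a listing of non-treatment-emergent SAEs.

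**Collection in long-term follow-up.** Protocol 4.1.4: "Participants will be followed for overall survival and subsequent anti-cancer therapy at 3-month intervals". SAP 4.5: "During the long term follow-up data on survival and subsequent anti-cancer therapies are collected by either telephone contact or onsite visit". Appendix 6 of the protocol describes the same two items. None of the three names AEs. SAP 4.5 also limits the long-term follow-up analysis to population characteristics, overall survival and anti-cancer medication.

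**Collection in active follow-up.** Protocol 8.3.1: "All AEs and SAEs will be collected from the signing of the ICF until the end of active FU visit", which it places at 30 days after regorafenib and 100 days after nivolumab. Appendix 6, on participants who stop treatment without radiological progression, says "drug-related AEs will continue to be collected". Protocol 4.1.3 likewise keeps following treatment-related toxicity until active follow-up is complete. For these participants that can be well past day 100, because scans continue.

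**The concern.** An incidence table implies that the events were looked for in everyone in its denominator. Here the only AE incidence table for the time after the post-treatment window covers a period with no described AE collection. The period in which two protocol sections say late drug-related AEs are still collected gets a listing, with no denominator and no rate.

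Safety of the combination is a secondary objective, and the protocol expects some delay with nivolumab: "These AEs may occur shortly after the first dose or several months after the last dose of treatment". An empty or nearly empty long-term table, carried into a study report, could be read as evidence that late toxicity did not occur. It would show only that nobody asked.

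**Working it through.** The plan states no late-toxicity figure to reproduce, so the check sets the collection rules beside the reporting rules, period by period.

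| Period | AE collection described | Planned output |
|---|---|---|
| Treatment plus the 30/100-day window | All AEs and SAEs (protocol 8.3.1, SAP 6.5.2) | TEAE tables, most of them split by relationship to each drug (SAP 6.5.2) |
| Active follow-up after the window | Drug-related AEs in participants without radiological progression (protocol 4.1.3, Appendix 6); none according to 8.3.1 | Listing only (SAP 6.5.2) |
| Long-term follow-up | None described (protocol 4.1.4, Appendix 6, SAP 4.5) | Incidence table (SAP 6.5.2) |

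The first row is consistent. The second and third are the wrong way round: an event in the second row is neither treatment-emergent nor in long-term follow-up, so it falls under the listing rule.

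**What an empty table would convey.** SAP 6.5 runs all safety analyses on the FAS, planned at 70 treated patients. With no events, the upper two-sided 95% Clopper-Pearson limit is 1 − 0.025^(1/n):

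- n = 70: 1 − 0.025^(1/70) = 1 − exp(−3.689/70) = 0.0513.
- The result would be 0%, interval 0 to 5.1%.

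That limit is valid only if events were ascertained in all 70. Without solicitation it bounds nothing of interest.

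**Events left to the listing.** The documents give neither the number of participants still in active follow-up after the window nor a late event rate. For scale only, assume 5 to 20 of the 70 remain and 5% to 20% of them have a late drug-related AE:

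- Low end: 5 × 0.05 = 0.25 participants, or 0.25/70 = 0.4%.
- High end: 20 × 0.20 = 4 participants, or 4/70 = 5.7%.

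Both inputs are assumptions, so the range is not an estimate for this trial.

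**The case against.** The strongest reply is that delayed toxicity is largely tabulated already. AEs starting up to 30 days after regorafenib or 100 days after nivolumab are TEAEs and enter the tables by drug relationship. Later events remain visible: they are listed by patient, non-treatment-emergent SAEs have their own listing, and deaths beyond the window are listed separately. With at most 70 patients, a listing for a small late subgroup is a defensible choice. All of this stands, and it limits the point to events after the window.

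A second reply is that late collection in active follow-up is not settled. Protocol 8.3.1 ends it at the 30/100-day visit, SAP 6.5.2 repeats that rule, and the Appendix 6 sentence is grammatically incomplete. This also stands. If sites stopped at that visit, a new table would suffer from uneven ascertainment too, so the sections must be reconciled before any table is added.

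Third, SAP 6.5.2 equates the end of active follow-up with the 30/100-day visit and gives no start date for long-term follow-up. On that usage, later events might count as long-term and be tabulated. This does not rescue the table. It would then pool participants still under AE collection with participants followed only for survival.

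Fourth, the extent of the AE-review arrow in the Schedule of Activities cannot be read in the extracted text, so it neither confirms nor refutes collection in long-term follow-up. It should be checked in the original layout. Protocol 8.3.1 also requires notice of related SAEs that the investigator learns of after a participant's discharge. Those are not actively sought, so they cannot support an incidence.

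A reader might go further and infer that the trial's delayed-toxicity rate is near zero by construction, or that late toxicity is understated by some large percentage. The documents do not support either. The SAP defines no delayed-toxicity rate, so only the one table is affected. Any percentage would merely restate an assumed capture rate for unsolicited reports.

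**Conclusion.** The mismatch between collection and reporting is in the text. As written, the long-term follow-up AE table would be empty or near zero by construction and open to misreading. Drug-related AEs starting after the 30/100-day window in active follow-up would appear only in a listing. This rests on taking the 30/100 days in SAP 6.5.2 as the post-treatment window, and on long-term follow-up collecting only what protocol 4.1.4, Appendix 6 and SAP 4.5 describe. Whether a usable body of late active follow-up data exists depends on which protocol section the sites followed.

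No numerical size can be given for an understatement. Severity is minor: the primary endpoint, its test and the main TEAE tables are unaffected.

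**What to change.** 1. In SAP 6.5.2, drop the incidence table for AEs in long-term follow-up. Put any such reports in a listing labelled as not solicited. This also brings 6.5.2 into line with SAP 4.5. Keep the pre-treatment AE table.
2. Reconcile protocol 8.3.1, and SAP 6.5.2 which repeats it, with protocol 4.1.3 and Appendix 6: are drug-related AEs collected after the 30/100-day visit, and in whom?
3. Where they were collected, tabulate drug-related AEs starting after the window during active follow-up. Use as denominator the participants still under AE collection after the window, and say in the title that this group is small and selected (off treatment without radiological progression).
4. State the post-treatment window in days within the TEAE definition, so that events after it are identified without inference.

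The cost is a SAP wording change, one table exchanged for another, and a protocol clarification. No new data are needed if late drug-related AEs were in fact collected. If they were not, step 3 falls away and the report should say that AEs were not sought after the window.
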